8.10.2 Biological Sample Retention and Destruction

Details of biological sample collection, handling, and analysis are presented in the laboratory manual. Repeat or unscheduled samples may be collected for safety reasons or for technical issues with the samples. Biological samples will be preserved and retained at a central laboratory that was contracted by the Sponsor for this purpose for up to but not longer than 20 years or as required by applicable law. The Sponsor has put into place a system to protect the participant's personal information to ensure optimal confidentiality and defined standard processes for sample and data collection, storage, analysis, and destruction.

8.11 Safety Assessments

All participants will be monitored for 30 minutes after study injection for any immediate AEs with appropriate medical treatment readily available in case it is needed.

- Local reactions and systemic solicited AEs ([Section 9.1.9](#)) will be recorded daily within 7 days after each study vaccination:
 - Local reactions: pain, erythema, and swelling at the injection site;
 - Systemic AEs: fatigue, headache, myalgia, arthralgia, nausea, dizziness, chills, and fever.
- Any unsolicited AEs will be collected within 28 days after each study vaccination ([Section 9.1.9](#));
- Pregnancies will be recorded throughout the study ([Section 9.1.13](#));

CONFIDENTIAL

- Any SAEs ([Section 9.1.2](#)), AESIs ([Section 9.1.14](#)), MAAEs ([Section 9.1.15](#)) and AEs leading to early study termination, will be reported during the entire study period. These data will be captured by interviewing the participant during the site visits and phone calls and by review of available medical records.
- Any diagnosed episodes of SARS-CoV-2 infection will be reported as MAAEs; no active surveillance for SARS-CoV-2 infection is planned in this study.

Refer to [Section 9.0](#) for safety definitions. This section contains details on collection ([Section 9.1.7](#)), follow-up ([Section 9.1.10](#)) and reporting of AEs ([Section 9.1.11](#)).

Planned time points for all safety assessments are provided in the SoA ([Table 1](#)).

8.12 Schedule of Assessments

8.12.1 Screening (Day 1)

All screening evaluations must be completed and reviewed to confirm that potential participants meet all eligibility criteria. The investigator will maintain a screening log to record details of all participants screened and to confirm eligibility or record reasons for screening failure, as applicable.

If all Screening procedures are performed prior to Day 1, the following Screening assessments should be repeated prior to dosing on Day 1: physical examination, vital signs, pregnancy testing, and testing for COVID-19.

8.12.2 Pre-vaccination Procedures (Day 1 and Day 29)

- Informed consent ([Section 8.1](#))*
- Demographics ([Section 8.2](#))*
- Medical history and prior medication ([Section 8.2](#))*
- Concomitant medications ([Section 5.4](#))
- Physical examination and vital signs ([Section 8.3](#))
- 12-lead electrocardiogram* and blood samples for cardiac enzymes testing* ([Section 8.6](#))
- Pregnancy test ([Section 8.4](#))
- Rapid COVID-19 antigen test or equivalent ([Section 8.5](#))
- Blood sampling for immunogenicity ([Section 8.10](#))

* Pre-vaccination procedure for Day 1 vaccination only.

8.12.3 Vaccination and Post-vaccination Procedures (Day 1 and Day 29)

Perform randomization ([Section 8.8](#)) at Visit 1 (Day 1).

After confirming eligibility ([Section 8.7](#)) at Visit 1 (Day 1) and at subsequent vaccination visit (Day 29), ensure that the participant does not meet criteria for delay or discontinuation ([Section 5.3](#)).

Perform vaccination ([Section 8.9](#)).

CONFIDENTIAL

The following post-vaccination procedures will be performed at Visit 1 (Day 1) and Visit 2 (Day 29):

- Participants will be observed for 30 minutes after vaccination in case of any adverse reaction. Any AEs reported within 30 minutes after vaccination will be recorded in the eCRF.
- After study vaccine administration, vital signs will be measured (BP, RR, body temperature, and heart rate) and vital sign measurement should be repeated if clinically indicated.

Careful training of the participant (or the individual who will be performing the measurements) on how to measure local reactions and body temperature, how to complete and how often to complete the eDiary will occur at Visit 1.

At Day 1, when two study vaccines will be co-administered, participant will be instructed to record local reactogenicity for both arms separately.

Specifically, participants in:

Groups 1a and 1b will receive: ARCT-2303 on the left arm and influenza vaccine on the right arm,

Groups 2a and 2b will receive: ARCT-2303 on the left arm and placebo on the right arm,

Groups 3a and 3b will receive: placebo on the left arm and influenza vaccine on the right arm.

At Day 29, vaccine administration will be done in the non-dominant arm.

eDiary instructions must include the following:

- The participant must understand that timely completion of the eDiary on a daily basis is a critical component to study participation.
- The participant should be instructed on how to complete the eDiary and how to make corrections to erroneous entries.
- Starting on the day of vaccination, the participant will check approximately 6 hours post-vaccination (minimum of 4 hours post-vaccination) for specific types of reactions at the injection site (solicited local adverse reactions), any specific generalized symptoms (solicited systemic AEs), body temperature (preferably axillary), any other symptoms or change in the participant's health status, and any medications taken.
- The participant must use the thermometer provided by the site for body temperature measurement. If the participant feels unusually hot or cold during the day, the participant should check body temperature several times and record the highest body temperature observed that day on the eDiary.
- The collection of body temperature, solicited local adverse reactions, and solicited systemic AEs will continue for a total of 7 days on the eDiary.

The eDiary will be the only source document allowed for solicited local reactions and systemic AEs (including body temperature measurements).

CONFIDENTIAL

May not be used, divulged, published or otherwise disclosed without written consent of Arcturus Therapeutics, Inc.

Note: Any solicited AE that meets any of the following criteria must be entered into participants' source document (see [Appendix 2](#)) and also as an AE on the AE CRF:

- Solicited local or systemic AEs leading to a visit to a healthcare provider (MAAE, [Section 9.1.15](#)).
- Solicited local or systemic AEs leading to the participant withdrawing from the study or the participant being withdrawn from the study by the investigator (AE leading to withdrawal; see [Section 7.1](#)).
- Solicited local or systemic AE that otherwise meets the definition of an SAE ([Section 9.1.2](#)).
- Solicited local or systemic AE that continues beyond 7 days post-vaccination.

Compliance checks for eDiary completion will be performed on Day 2 (± 1) and Day 5 (± 1) after each vaccination. The site will perform a check to verify that the participant has completed the eDiary. Participants will be contacted by telephone if the eDiary is incomplete. Compliance checks will be documented in the source.

8.12.4 Non-vaccination Site Visit Procedure (Day 57)

Site visit that does NOT include a vaccination will be performed on Day 57. The following procedures will be completed as planned in the SoA ([Table 1](#)):

- Symptom-directed physical examination and vital signs
- Review of eDiary
- Adverse events collection
- Concomitant medications/vaccines collection

The site should schedule the next site visit or other study activity with the participant.

8.12.5 Phone Contact (Day 91)

A safety call will be made by phone contact (PC) on Day 91 for collection of any signs and symptoms the participant may have experienced, any new diagnosed medical conditions, and medications taken since the previous contact. This call will follow a script and will be made by trained healthcare personnel.

A trained healthcare professional is defined as any healthcare professional permitted by institutional policy and trained to perform delegated tasks, trained on the study procedure(s), and identified within the site signature and delegation log.

Any safety information collected during the phone contact will be entered into the source documents, and any medically attended AEs, SAEs, AESIs, and AEs leading to early study termination and related medications and any vaccinations will be reported in the eCRF, as appropriate.

8.12.6 End-of-study (Day 181) or Early Termination (ET)/Last Visit Procedures

The final (end-of-study) contact will be performed on Day 181. If a participant terminates earlier, the ET visit procedures should be performed at their last study visit, if possible. See the SoA ([Table 1](#)) for data to be collected at the end-of-study and an early termination visit. The

CONFIDENTIAL

investigator must complete the end-of-study CRF page for all participants who received the study vaccine.

8.12.7 Unscheduled Visits

Unscheduled visits include visits for possible COVID-19 episodes, possible cardiac events, or evaluation of any adverse event of concern. These visits may be performed in the clinic, by home visit, by hospital visit (if allowed by local policy), or via telemedicine/telephone visit. Required procedures at these visits include AE and concomitant medication collection. Should the visit occur in person, the visit should also include evaluation of vital signs, and symptom-directed physical examination.

For participants with suspected SARS-CoV-2 infection, nasal or nasopharyngeal samples may be collected for RT-PCR testing.

For participants evaluated for cardiac symptoms, 12-lead electrocardiogram and targeted safety laboratory assessments should be performed. If myocarditis or pericarditis is suspected based on investigator evaluation of the participant, the participant should be referred to a cardiologist, ideally within 24 hours (see [Section 9.1.14.1](#)).

A blood sample might be drawn for additional laboratory safety evaluation, including cardiac enzymes, as per investigator discretion.

Additional safety phone calls may be performed as a follow-up for the evaluation of adverse event(s) or SARS-CoV-2 infection.

8.12.8 Post-study Procedures

Any SAE that occurs outside of the protocol-specified observation period or after the end of the study but is considered to be caused by the study vaccine will be processed by the Sponsor (or delegate) and must be reported to the Sponsor.

Any post-study pregnancy-related SAE considered reasonably related to the study vaccine by the investigator will be reported to the Sponsor. While the investigator is not obligated to actively seek this information in former participants, he or she may learn of an SAE through routine medical practice.

These SAEs and pregnancy information will be considered as part of the spontaneous reporting towards the investigational study vaccine in order to ensure the safety of all participants.

No post-study care will be provided.

CONFIDENTIAL

9 ADVERSE EVENTS

The following sections provide definitions for AEs, the procedures for collecting, following up and reporting to the authorities.

AEs will be reported by the participant (or, when appropriate, by a caregiver) or identified at study visit.

The investigator and any designees are responsible for detecting, documenting, and recording events that meet the definition of an AE or SAE and remain responsible for following up AEs that are serious, considered related to the study vaccine or study procedures, or that caused the participant to discontinue the study (see [Section 7](#)).

9.1 Definitions

9.1.1 Definition of an Adverse Event

- An AE is any untoward medical occurrence in a participant or participant administered a medicinal product, whether or not considered related to the study vaccine.
- NOTE: An AE can therefore be any unfavorable and unintended sign (including an abnormal laboratory finding), symptom, or disease (new or exacerbated) temporally associated with the use of a medicinal product.

9.1.1.1 Events Meeting the AE Definition

- Any abnormal laboratory test results (hematology, clinical chemistry, or urinalysis) or other safety assessments (e.g., electrocardiogram, radiological scans, or vital signs measurements), including those that worsen from baseline, considered clinically significant in the medical and scientific judgment of the investigator.
- Exacerbation of a chronic or intermittent pre-existing condition including either an increase in frequency and/or intensity of the condition.
- New conditions detected or diagnosed after study vaccine administration even though it may have been present before the start of the study.
- Signs, symptoms, or the clinical sequelae of a suspected drug-drug interaction.

9.1.1.2 Events NOT Meeting the AE Definition

- Any clinically significant abnormal laboratory findings or other abnormal safety assessments which are associated with the underlying disease, unless judged by the Investigator to be more severe than expected for the participant's condition.
- Medical or surgical procedure (e.g., endoscopy, appendectomy): The condition that leads to the procedure is the AE.
- Situations in which an untoward medical occurrence did not occur (social and/or convenience admission to a hospital).
- Anticipated day-to-day fluctuations of pre-existing disease(s) or condition(s) present or detected at the start of the study that do not worsen.

CONFIDENTIAL

- Pre-existing conditions or signs and/or symptoms present in a participant prior to the first study vaccination. These events will be recorded in the medical history section of the eCRF.

9.1.2 Definition of an SAE

An SAE is defined as any AE that, at any dose:

- a) Results in death.
- b) Is life-threatening.
- c) Requires inpatient hospitalization or prolongation of existing hospitalization.

In general, hospitalization signifies that the participant has been detained (usually involving at least an overnight stay) at the hospital or emergency ward for observation and/or treatment that would not have been appropriate in the physician's office or outpatient setting. Complications that occur during hospitalization are AEs. If a complication prolongs hospitalization or fulfills any other serious criteria, the event is serious. When in doubt as to whether "hospitalization" occurred or was necessary, the AE should be considered serious.

Hospitalization for elective treatment of a pre-existing condition that did not worsen from baseline is not considered an AE.

- d) Results in persistent disability/incapacity.
 - The term disability means a substantial disruption of a person's ability to conduct normal life functions.
 - This definition is not intended to include experiences of relatively minor medical significance such as uncomplicated headache, nausea, vomiting, diarrhea, influenza, and accidental trauma (e.g., sprained ankle) which may interfere with or prevent everyday life functions but do not constitute a substantial disruption.
- e) Is a congenital anomaly/birth defect.
- f) Is a medically important event:
 - Medical or scientific judgment should be exercised in deciding whether SAE reporting is appropriate in other situations such as important medical events that may not be immediately life-threatening or result in death or hospitalization but may jeopardize the participant or may require medical or surgical intervention to prevent one of the other outcomes listed in the above definition. These events should usually be considered serious.
 - Examples of such events include invasive or malignant cancers, intensive treatment in an emergency room or at home for allergic bronchospasm, blood dyscrasias, or convulsions that do not result in hospitalization, or development of drug dependency or drug abuse.

CONFIDENTIAL

9.1.3 Recording of AEs and SAEs

- When an AE occurs, it is the responsibility of the investigator to review all documentation (e.g., hospital progress notes, laboratory reports, and diagnostics reports) related to the event.
- The investigator will then record all relevant AE information in the eCRF. Each event must be recorded separately.
- It is not acceptable for the investigator to send photocopies of the participant's medical records to the Sponsor/Sponsor's designee in lieu of completion of the relevant eCRF page.
- There may be instances when copies of medical records for certain cases are requested by the Sponsor/Sponsor's designee. In this case, all participant identifiers, with the exception of the participant number, will be redacted on the copies of the medical records before submission to the Sponsor/Sponsor's designee.
- The investigator will attempt to establish a diagnosis of the event based on signs, symptoms, and/or other clinical information. Whenever possible, the diagnosis (not the individual signs/symptoms) will be documented as the AE.

9.1.4 Assessment of Intensity

The investigator will make an assessment of intensity for each AE reported during the study and assign it to 1 of the following categories, based on the [US Food and Drug Administration \(FDA\) Toxicity Grading Scale for Healthy Adult and Adolescent Volunteers Enrolled in Preventive Vaccine Clinical Trials](#):

- Mild (Grade 1): transient with no limitation in normal daily activity
- Moderate (Grade 2): some limitation in normal daily activity
- Severe (Grade 3): unable to perform normal daily activity
- Potentially Life-Threatening (Grade 4): an event in which the participant was at immediate risk of death at the time of the event
- Fatal (Grade 5): an event with a fatal outcome

Note: An event is defined as 'serious' when it meets at least 1 of the predefined outcomes as described in the definition of an SAE, NOT when it is rated as severe. Severe is a category utilized for rating the intensity of an event; and both AEs and SAEs can be assessed as severe.

9.1.5 Assessment of Causality

- The investigator is obligated to assess the relationship between study vaccine and each occurrence of each AE. The AE must be characterized as related or unrelated:
- **Related:** An AE that followed a temporal sequence from administration of a drug (including the course after withdrawal of the drug), or for which possible involvement of the drug could not be ruled out, although factors other than the drug, such as underlying diseases, concurrent medical conditions, concomitant drugs, and concurrent treatments, were also responsible.

CONFIDENTIAL

- **Unrelated:** An AE that did not follow a temporal sequence from study administration of a drug and/or that could reasonably be explained by other factors, such as underlying diseases, concurrent medical conditions, concomitant drugs, and concurrent treatments.
- The investigator will use clinical judgment to determine the relationship.
- Alternative causes, such as underlying disease(s), concomitant therapy, and other risk factors, as well as the temporal relationship of the event to study vaccine administration will be considered and investigated.
- The investigator will also consult the IB and product information, for marketed products, in his/her assessment.
- For each AE/SAE, the investigator must document in the medical notes that he/she has reviewed the AE/SAE and has provided an assessment of causality.
- There may be situations in which an SAE has occurred and the investigator has minimal information to include in the initial report to the Sponsor/Sponsor's designee. However, it is very important that the investigator always make an assessment of causality for every event before the initial transmission of the SAE data to the Sponsor/Sponsor's designee.
- The investigator may change his/her opinion of causality in light of follow-up information and send a SAE follow-up report with the updated causality assessment.
- The causality assessment is one of the criteria used when determining regulatory reporting requirements.

9.1.6 Assessment of Outcome of AE

The investigator will assess the outcome of all AEs recorded during the study as:

- Recovered/resolved.
- Recovering/resolving.
- Not yet recovered/not yet resolved.
- Recovered with sequelae/resolved with sequelae.
- Fatal (all fatal events are considered SAEs and should be reported accordingly).
- Unknown.

9.1.7 Time Period and Frequency for Collecting Adverse Event and Serious Adverse Event Information

Medical occurrences that begin before the study vaccination but after obtaining informed consent will be recorded in the medical history/current medical conditions section of the eCRF, not the AE section. Exacerbation of a chronic or intermittent pre-existing condition including either an increase in frequency and/or intensity of the condition after the first vaccination will be considered an AE.

For all participants:

- Any unsolicited AEs will be collected within 28 days after each vaccination.
- Any AEs that occur within 30 minutes after study vaccination are to be reported in the eCRF.
- Any AEs that are determined by the investigator (or designee) to be SAEs, AESIs (serious and nonserious), MAAEs, or AEs leading to early termination from the study or
CONFIDENTIAL

study vaccination (regardless of the causal relationship) are to be reported in the eCRF from the moment of first vaccination until completion of the participant's last study-related procedure, which may include contact for safety follow-up (until the end of the study).

All AESIs and SAEs will be recorded and reported to the Sponsor or the Sponsor's designee immediately and under no circumstance should this exceed 24 hours after the investigator becomes aware of it. The investigator will submit any updated data to the Sponsor within 24 hours of it being available.

9.1.8 Method of Detecting AEs and SAEs

The method of recording, evaluating, and assessing intensity, causality and outcome of AEs and SAEs and the procedures for completing and transmitting AESI/SAE reports are provided in [Section 9.1.7](#), [Section 9.1.11](#) and [Section 9.1.14](#).

Care will be taken not to introduce bias when detecting AEs and/or SAEs. Open-ended and non-leading verbal questioning of the participant is the preferred method to inquire about AE occurrences.

9.1.9 Solicited and Unsolicited Adverse Events

The investigator or designee will review and verify the completed eDiary during discussions with the participant as per the time points detailed in the SoA.

Participants will record solicited AEs and a presence of unsolicited AEs in the eDiary. The investigator or designee will review the eDiary entries and collect the details of the unsolicited AEs with the participant. The investigator or designee will then transcribe the appropriate collected information into the relevant eCRF pages, according to the guidance presented in [Section 9.1.7](#). If the AE meets AESI criteria or SAE criteria, it should also be reported to the Sponsor or Sponsor's designee ([Section 9.1.11](#)).

Solicited local (injection site) reactions:

- Injection site pain
- Erythema
- Swelling

Solicited systemic AEs:

- Fatigue
- Headache
- Myalgia
- Arthralgia
- Nausea
- Dizziness
- Chills
- Fever ($\geq 38.0^{\circ}\text{C}$; axillary)

Severity grading for these AEs is presented in [Table 7](#).

CONFIDENTIAL

Table 7 Severity Grading for Solicited Local Reactions and Systemic Adverse Events

| | Mild | Moderate | Severe |
|-------------------|---------------------------------------|----------------------------------|-------------------------|
| Pain | No interference with daily activities | Interferes with daily activities | Prevents daily activity |
| Erythema | 25-50 mm | 51-100 mm | > 100 mm |
| Swelling | 25-50 mm | 51-100 mm | > 100 mm |
| Fatigue | No interference with daily activities | Interferes with daily activities | Prevents daily activity |
| Headache | No interference with daily activities | Interferes with daily activities | Prevents daily activity |
| Myalgia | No interference with daily activities | Interferes with daily activities | Prevents daily activity |
| Arthralgia | No interference with daily activities | Interferes with daily activities | Prevents daily activity |
| Nausea | No interference with daily activities | Interferes with daily activities | Prevents daily activity |
| Dizziness | No interference with daily activities | Interferes with daily activities | Prevents daily activity |
| Chills | No interference with daily activities | Interferes with daily activities | Prevents daily activity |
| Fever (°C) | 38.0-38.4 | 38.5-38.9 | ≥39.0 |

Note: Based on [Food and Drug Administration \(FDA\) Guidance Document: Toxicity Grading Scale for Healthy Adult and Adolescent Volunteers Enrolled in Preventive Vaccine Clinical Trials](#).

Unsolicited AEs

An unsolicited AE is an AE that is not listed as 'solicited' above.

Potential unsolicited AEs may be medically attended (defined as symptoms or illnesses requiring hospitalization, or emergency room visit, or visit to/by a healthcare provider; [Section 9.1.15](#)) or were of concern to the participants. In case of such events, participants will be instructed to contact the study center as soon as possible to report the event(s). The detailed information about the reported unsolicited AEs will be collected by the qualified study center personnel during the interview and will be documented in the participant's records.

Unsolicited AEs that are not medically attended or perceived as a concern by participants will be collected during planned safety visits/contacts with the participants and by review of available medical records.

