| 1. To assess the safety and reactogenicity of the study vaccines when given in co-administration or standalone | 
 • Local and systemic AEs reported within 7 days after each study vaccination • Unsolicited AEs reported within 28 days after each vaccination • SAE, AEs leading to early termination from study, MAAEs, and AESIs during the entire study period (6-month follow-up) | 
 • Proportion of participants with local and systemic solicited AEs; • Proportion of participants with unsolicited AEs; • Proportion of participants with SAEs; • Proportion of participants with MAAEs; • Proportion of participants with AESIs; • Proportion of participants with AEs leading to early termination from study; by Safety set. |

CONFIDENTIAL

Table 4 Objectives, Endpoints and Estimands

| Exploratory Immunogenicity Objectives | | |
|--|---|--|
| 1. To assess the immune response elicited by the ARCT-2303 vaccine against a panel of SARS-CoV-2 strains, as measured by VNA | SARS-CoV-2 neutralizing antibody responses with a panel of historical and new emergent SARS-CoV-2 strains on Days 1 and 29 in a subset of: 
• Standalone ARCT-2303 group recipients (Group 2a and/or 2b)• Standalone QIV group recipients (Group 3a and/or 3b) | 
• GMTs• GMFRs (post/pre-vaccination)• SCRs• Proportion of participants with antibody titer \geq LLOQ by PP set for immunogenicity. |
| 2. To assess the immunogenicity of influenza vaccine(s) when administered with or without ARCT-2303 as measured by microneutralization assay (in a subset of participants) | Microneutralization (MN) titers against influenza vaccine strains on Day 1 and Day 29, in: 
• Co-admin group recipients (a subset of participants from Group 1a and/or 1b)• Standalone QIV group recipients (a subset of participants from Group 3a and/or 3b). | 
• GMTs• GMFRs (post/pre-vaccination)• SCRs• Proportion of participants with antibody titer \geq LLOQ 
For each influenza vaccine strain, by PP set for immunogenicity.
 |

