9.1.14.1 Suspected Myocarditis and Pericarditis Cases

All suspected cases of myocarditis, pericarditis, and myopericarditis should be reported to the Sponsor in an expedited manner.

CONFIDENTIAL

All study participants should be instructed to report to site personnel, as soon as possible, a new onset of chest pain, shortness of breath (at rest or during activity), rapid or irregular heartbeat (arrhythmias), swelling of the legs, ankles, and feet, light-headedness, collapse, and fatigue occurring within 6 weeks after each vaccination.

The investigator must perform the initial assessment of the study participant with these symptoms/signs and refer individuals with suspected myocarditis and pericarditis to a cardiologist for evaluation and management, ideally within 24 hours of assessment by site. A questionnaire will be provided to the investigators for assessment of suspected cases. A 12-lead ECG and cardiac enzyme testing should be performed in all participants with suspected myocarditis and pericarditis. Additional evaluations (such as echocardiography, cardiac MRI) might be performed based on the cardiologist's recommendations.

A central cardiac adjudication committee will assess all suspected cases of myocarditis and pericarditis (as determined by investigator and cardiologist) according to the Brighton Collaboration case definition ([Sexson Tejtel et al, 2021](#)) within 1 week of the initial reporting.

Cases of myocarditis and/or pericarditis will be followed until resolution of abnormal test findings and symptoms.

Cases of myocarditis and/or pericarditis occurring in temporal association with vaccination will be considered potentially related, unexpected, and serious, and are subject to expedited reporting requirements as outlined in [Section 9.1.11](#).

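### Unsolicited AEs are defined by term alone, so a minor solicited-list symptom that first appears on Days 8-28 after a vaccination belongs, as written, to neither safety endpoint

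*Protocol*

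**What the plan says.** Protocol section 9.1.9 lists three local reactions (pain, erythema, swelling) and eight systemic AEs (fatigue, headache, myalgia, arthralgia, nausea, dizziness, chills, fever). It gives no onset limit with the list. It then states: "An unsolicited AE is an AE that is not listed as 'solicited' above".

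The time windows are set elsewhere:

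- Protocol 8.11: solicited events "will be recorded daily within 7 days after each study vaccination".
- Protocol 8.12.3: "The collection of body temperature, solicited local adverse reactions, and solicited systemic AEs will continue for a total of 7 days on the eDiary".
- Protocol section 3, Table 4, secondary safety endpoints: "Local and systemic AEs reported within 7 days after each study vaccination" and "Unsolicited AEs reported within 28 days after each vaccination".

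Section 8.12.3 also says when a solicited AE must be entered on the AE CRF as well. There are four triggers: it led to a healthcare visit, it led to withdrawal, it meets the SAE definition, or it is a "Solicited local or systemic AE that continues beyond 7 days post-vaccination".

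SAP 7.1 uses the AE CRF for solicited terms only to obtain the stop date of events that outlast the diary. SAP 7.2 tabulates the unsolicited AEs held on the AE CRF. It neither defines the word nor says what to do with a listed symptom that began late.

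**The concern.** One of the two categories is bounded by time and the other by name, and together they do not cover all AEs. A participant who first has a headache on Day 12 has no diary day to enter it on, and the headache is on the solicited list, so 9.1.9 says it is not unsolicited.

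What is at stake is the meaning of a named secondary safety endpoint, the proportion of participants with unsolicited AEs within 28 days of each vaccination. The AE CRF will also hold solicited events that ran past Day 7, so whoever builds the SAP 7.2 tables has to separate solicited from unsolicited entries there. The only definition available for that task removes late-onset listed symptoms. Someone following usual practice would keep them. Two people working from the same plan could produce different rates.

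**Working it through.** No power, sample size or alpha figure is involved, and the plan states no figure to reproduce. The check sets the rules side by side and follows one event through them: a mild headache first felt on Day 12 after the Day 1 vaccination, with no healthcare visit.

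| Rule | Does it place the event? |
|---|---|
| Solicited endpoint (Table 4; 8.11; SAP 7.1) | No. Onset is after the 7 days. |
| Unsolicited endpoint (Table 4; 9.1.9; SAP 7.2) | Not as defined. Headache is on the list. |
| 8.12.3 trigger: healthcare visit | No |
| 8.12.3 trigger: withdrawal | No |
| 8.12.3 trigger: serious | No |
| 8.12.3 trigger: continues beyond 7 days | No. It did not begin within the 7 days. |
| 9.1.7: AEs within 30 minutes of vaccination | No |
| 9.1.7: SAE, AESI, MAAE, or AE leading to early termination | No |
| General AE duties (9, 9.1.1, 9.1.3) | Yes for recording. They do not say which table it enters. |

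If one attribute changes, the event is caught. If it is medically attended, serious, an AESI or a cause of withdrawal, 9.1.7 requires it to be reported throughout the study, and SAP 7.2 has a separate summary for each of these. The gap is therefore limited to minor events.

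**Length of the gap**

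- Unsolicited window per vaccination: 28 days (Table 4; 9.1.7).
- Solicited window per vaccination: 7 days (Table 4; 8.11; 8.12.3).
- Difference: 28 - 7 = 21 days, and 21/28 = 75% of the window.
- Two vaccination visits (Day 1 and Day 29): 2 x 21 = 42 of 2 x 28 = 56 days.
- Terms affected: 3 + 8 = 11.

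The 75% is a share of calendar time, not of events. Neither document gives a frequency for listed symptoms that start after Day 7, so no number of events or participants can be derived.

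**The case against.** The strongest reply is that the protocol ties solicited events to the 7-day eDiary wherever it describes their collection, and that 8.12.3 makes the eDiary their sole permitted source. On that reading, an event that first arises after the diary closes is not solicited and defaults to unsolicited. SAP 7.2 states no filter that would remove it. This is a sensible reading and probably the intended one. But no sentence says so: the passages on the diary set a collection period, while 9.1.9 is the only definition and it goes by term. The continuation trigger in 8.12.3 does not settle the matter, because an event that began within the 7 days would stay solicited on either reading.

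Three further inferences might tempt a reader. The documents do not support them.

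- **That sites would not record the event.** Section 9 makes investigators responsible for documenting whatever meets the AE definition, 9.1.1 defines an AE without reference to either label, and 9.1.3 requires AE information to go into the eCRF. AEs are also reviewed at the Day 29 and Day 57 visits. What is missing is the classification.
- **That a cardiac signal could be lost.** Section 9.1.14.1 instructs participants to report a set of symptoms including "light-headedness, collapse, and fatigue occurring within 6 weeks after each vaccination", and the investigator must assess them. Section 9.1.14 asks for symptoms that might represent an AESI to be recorded as AEs.
- **That the earlier trial shows the size of the loss.** Protocol 2.1.2 gives 40.9% of placebo recipients with a solicited systemic AE and 14.0% of participants with an unsolicited AE. The first covers two vaccinations in the placebo arm; the second follows the first vaccination in the ARCT-154 arm. The placebo figures for unsolicited AEs are 13.7% and 15.9% after the first and second vaccinations. None of these concerns onset after Day 7.

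It is also true that the same rule would apply to all blinded, randomised arms, and that safety has no hypothesis test (Protocol 10.1).

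**Conclusion.** The point holds as a defect of definition. As written, a listed symptom with first onset on Days 8-28 counts in neither the solicited nor the unsolicited endpoint, provided it is non-serious, not medically attended, not an AESI and not a cause of withdrawal. The period is 21 of 28 days after each vaccination, for all 11 terms; the effect on reported rates is unknown.

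The conclusion rests on reading 9.1.9 literally and on the absence of a later-onset rule anywhere in the protocol or SAP. The expected harm is inconsistent classification, and so a 28-day unsolicited AE rate whose content depends on who applied the definition. Different handling between sites or programmers is a possibility that the text leaves open, not something that the documents show to have happened.

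No primary objective, power figure or testing step is affected. The point merits correction because the endpoint is named in the objectives table and the remedy is small.

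**What to change.** Make three matching changes:

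1. **Protocol 9.1.9.** Define an unsolicited AE as any AE whose term is not on the solicited list, or whose term is on the list but whose onset falls after the 7-day solicited period.
2. **Protocol 8.12.3.** Add onset after the 7-day solicited period as a further reason to enter a listed symptom on the AE CRF.
3. **SAP 7.2.** State that listed symptoms on the AE CRF with onset after the 7-day period are counted in the 28-day unsolicited tables, and that events which began within the 7 days and continued remain solicited.

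The protocol changes fit in a clarification memo or the next amendment. If data collection has finished, the SAP sentence alone still settles how events already on the AE CRF are counted.

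The cost is slightly more AE entries at sites and a somewhat higher reported unsolicited AE rate. The changes concern recording and tabulation only.
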